12. STATISTICS

12.1 Statistical and Analytical Plans

Clinical data collected throughout the study will be analyzed by descriptive statistics to assess the study objectives. Descriptive statistics will be provided in summary tables according to the type of variable summarized:

- Quantitative variables will be summarized by using n (sample size), arithmetic mean, standard deviation (SD), median, minimum and maximum.
- Categorical variables will be summarized by using frequency distribution and percentages.

The design of the proposed study does not involve randomization, so no pre-defined subgroups of subjects are planned to be enrolled.

For time-to-event variables, cumulative freedom from event will be evaluated using Kaplan-Meier (KM)

method. The degree of uncertainty will be expressed with 95% confidence limits (calculated per the method proposed by Greenwood). KM graphs will be presented along with the number of case-at-risk at exact time points.

Unless otherwise specified, the significance level used for other statistical testing (for descriptive purposes) will be 0.05 and two-sided tests will be used.

The Statistical Analysis Plan (SAP) could be issued before database lock with more technical and detailed elaboration of the principal features of statistical analyses. Any deviations from the original statistical plan (including unplanned analyses) will be documented in the Clinical Study Report.

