14 STATISTICAL ANALYSIS METHODS

The methods of analysis to be used for both objectives of the study and for description of the study variables are detailed below.

Quantitative variables will be described with measures of central tendency and dispersion: mean, median, SD (standard deviation), Q1 (first quartile) and Q3 (third quartile), minimum and maximum. Qualitative variables will be described using absolute and relative frequencies.

In the descriptive analysis of qualitative variables, two percentage columns will be presented, total percentage (%) and valid percentage (% valid), that are respectively, the percentage over the sum of valid responses plus missing values and the percentage over the total of valid responses.

Clopper-Pearson confidence intervals at 95.0% will be shown for the primary and secondary objectives.

For time-to-event variables (i.e. fracture free-survival) will be analysed using the Kaplan-Meier method. The median and the 95% CI as well as the number of events and patients censored will be provided. Error standard will be estimated per the method Greenwood (Greenwood, 1926). KM graphs will be presented along with the number of case-at-risk at exact time points.

Change in Gillette Functional Assessment Questionnaire from Screening to 1 year follow up will be analysed by means of descriptive statistics as a continuous variable. Comparisons will be performed by means of paired t-test (parametric) or Wilcoxon (non-parametric) depending on the distribution of the sample.

These tests will be used in all bilateral cases and with a level of significance of 0.05. In cases where a p-value less than 0.05 appears, it refers to the existence of statistical significance.

No imputation for missing data will be considered.

No adjustment for multiple comparisons will be performed.

Data will be analysed using SPSS v29.0 or later.

Interim Analysis: No interim analysis is planned.

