24.2 BONE UNION ACHIEVEMENT

The categorical variables to be described are, N and (%) and Clopper-Pearson confidence intervals will be shown at 95.0% as well, for the overall population and for subgroups of patients defined according to OI Type Diagnosis (Mild/Non-deforming / Severe / Highly Severe/Progressively deforming / Lethal) as defined in section 15.6 of this document:

- Number of procedures that reached a satisfactory bone consolidation in any visit (considering at the first visit in which the answer is “Yes” in “Has the bone reached a satisfactory consolidation?” variables in removal or bone consolidation visits)
- Number of patients that reached a satisfactory bone consolidation in any visit or procedure (considering at the first visit in which the answer is “Yes” in “Has the bone reached a satisfactory consolidation?” variables in removal or bone consolidation visits)

The descriptive statistic (Mean, SD, Median, Q₁, Q₃, Min, Max) will be shown for the following continuous variable, for the overall population and for subgroups of patients defined according to OI Type Diagnosis (Mild/Non-deforming / Severe / Highly Severe/Progressively deforming / Lethal) as defined in section 15.6 of this document:

- Time to full a satisfactory bone consolidation from surgery (months), per procedure, considering at the first visit in which the answer is “Yes” in “Has the bone reached a

satisfactory consolidation?" variables in removal or bone consolidation visits. Calculated as date of first consolidation minus date of surgery.

A list with bone consolidation variables will be shown.

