24.3 POST TREATMENT FRACTURE-FREE SURVIVAL

The categorical variables to be described are, N and (%) and Clopper-Pearson confidence intervals will be shown at 95.0% as well, for the overall population and for subgroups of patients defined according to OI Type Diagnosis (Mild/Non-deforming / Severe / Highly Severe/Progressively deforming / Lethal) as defined in section 15.6 of this document:

- Number of patients with fracture(s) occurred (variable: "Bone fracture during or after treatment" in adverse event description + confirmation that the bone with fracture is the same where there is the implant*) in at least one procedure
- Number of procedures with fracture(s) occurred (variable: "Bone fracture during or after treatment" in adverse event description + confirmation that the bone with fracture is the same where there is the implant*)

* A list, with confirmation for each AE that the "fracture" is on the same bone or not, will be provided from Sponsor in order to confirm if the bone with fracture is the same where there is the implant.

The descriptive statistic (Mean, SD, Median, Q₁, Q₃, Min, Max) will be shown for the following continuous variable, for the overall population and for subgroups of patients defined according to OI Type Diagnosis (Mild/Non-deforming / Severe / Highly Severe/Progressively deforming / Lethal) as defined in section 15.6 of this document:

- Time to free fracture from surgery (months), per procedure, considered at the first Adverse Event onset date in which variable: "Bone fracture during or after treatment" in adverse event description has been checked. Calculated as the first adverse event onset date with a "Bone fracture during or after treatment" minus date of surgery.

Kaplan-Meier analyses will be provided for Time to free fracture. The median and the 95%CI as well as the number of events and patients censored will be provided.

The number of patients at risk will be displayed.

Event: if "Bone fracture during or after treatment" in adverse event description is clicked (which first occurs).

Time: Time to free fracture from surgery, as has been defined above.

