24.4 WEIGHT BEARING GRADE

The categorical variables to be described are, N and (%) and Clopper-Pearson confidence intervals will be shown at 95.0% as well, for the overall population and for subgroups of patients defined according to OI Type Diagnosis (Mild/Non-deforming / Severe / Highly Severe/Progressively deforming / Lethal) as defined in section 15.6 of this document:

- Number of procedures that reached a Full weight-bearing (FWB) from surgery in any visit
- Number of Patients that reached a Full weight-bearing (FWB) from surgery in any visit or procedure

The descriptive statistic (Mean, SD, Median, Q₁, Q₃, Min, Max) will be shown for the following continuous variable, for the overall population and for subgroups of patients defined according to OI Type Diagnosis (Mild/Non-deforming / Severe / Highly Severe/Progressively deforming / Lethal) as defined in section 15.6 of this document:

- Time to Full weight-bearing from surgery (months), per procedure, considered at the first date in which the answer is "Full weight-bearing (FWB)" in "Weight bearing protocol assigned" variables. Calculated as date of the first visit of Full weight-bearing minus date of surgery.

A list with Weight bearing grade variables will be shown.

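### Times to consolidation and to full weight-bearing are summarised only over procedures that reach the event, so they tend to be short and do not register failed healing

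*SAP*

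**What the plan says.** **Consolidation (SAP 24.2).** The variable is "Time to full a satisfactory bone consolidation from surgery (months), per procedure". It is described by mean, SD, median, quartiles and range, overall and by OI severity group. It is "Calculated as date of first consolidation minus date of surgery", where first consolidation means the first Yes at the removal visit or the bone consolidation visit.

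**Weight-bearing (SAP 24.4).** "Time to Full weight-bearing from surgery (months), per procedure" receives the same statistics and is "Calculated as date of the first visit of Full weight-bearing minus date of surgery".

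**Fracture (SAP 24.3).** "Time to free fracture from surgery (months), per procedure" is also described by mean and median, but here a Kaplan-Meier analysis is added.

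**General rules.** Protocol 12.1 says: "For time-to-event variables, cumulative freedom from event will be evaluated using Kaplan-Meier (KM", with Greenwood limits, and does not restrict this to one variable. SAP 14 narrows it: "For time-to-event variables (i.e. fracture free-survival) will be analysed using the Kaplan-Meier method". SAP 14 also states: "No imputation for missing data will be considered". Neither 24.2 nor 24.4 has a censoring rule.

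**The concern.** The SAP does not say that these times are restricted to procedures that reach the event, but nothing else can be computed. The derivation needs an event date, and a missing date is not replaced. Four kinds of procedure can therefore be left out of the consolidation time:

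- those that never unite;
- those whose first satisfactory consolidation is seen only at the 9- or 12-month visit;
- those lost before consolidation is recorded;
- those whose nail is removed first, since Protocol 7.2 ends a case at implant removal.

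For weight-bearing, children who never reach full weight-bearing are left out. The SAP expects some of them: sections 19.2, 20.2 and 21.2 provide a field to explain why a child cannot stand although the bone is consolidated.

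The result is a time conditional on success. It tends to be short and does not move when more procedures fail. The severity-group summaries have the same weakness: if more severe types unite less often, more of their procedures drop out.

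**Working it through.** **Plan's own figures.** The documents give no figure for either time. Protocol 12.3 gives 20 evaluable procedures, 25 with 20% non-evaluable (20 / 0.80 = 25), and an assumed union rate of 80%.

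**How many procedures have no consolidation time.** At 80% union, 0.20 × 20 = 4. With the literature range for non-union or delayed union in Protocol 11.1.6 (8.47% to 36%), 0.0847 × 20 = 1.7 and 0.36 × 20 = 7.2, so about 2 to 7 of 20.

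**Illustration.** Assumptions: consolidation is recorded at the nominal 2 or 5 months (Protocol 10.2.4 and 10.2.5), 16 of 20 unite, split evenly, and the other 4 are followed to 12 months without union. The split between visits is not in the documents.

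- SAP mean: (8 × 2 + 8 × 5) / 16 = 56 / 16 = 3.5 months. SAP median: 3.5 months.
- Kaplan-Meier on all 20, proportion not yet united: 1.0 up to 2 months, 0.6 from 2 to 5, 0.2 from 5 to 12. Median: 5 months.
- 12-month restricted mean: 2 × 1.0 + 3 × 0.6 + 7 × 0.2 = 5.2 months. Restricted to 7 months: 2 + 1.8 + 2 × 0.2 = 4.2.

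**Varying the split and the failure rate (n = 20).**

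| United at 2 / 5 months | Not united | SAP mean | SAP median | KM median | 12-month restricted mean |
|---|---|---|---|---|---|
| 4 / 12 | 4 | 4.25 | 5 | 5 | 5.8 |
| 8 / 8 | 4 | 3.5 | 3.5 | 5 | 5.2 |
| 12 / 4 | 4 | 2.75 | 2 | 2 | 4.6 |
| 9 / 9 | 2 | 3.5 | 3.5 | 5 | 4.35 |
| 6 / 6 | 8 | 3.5 | 3.5 | 5 | 6.9 |

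With 4 not united, the gap in means is 1.55 to 1.85 months. The last two rows show the insensitivity: as failures rise from 10% to 40%, the SAP mean stays at 3.5 while the restricted mean goes from 4.35 to 6.9. If all 20 unite by 5 months, the two means are equal.

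**Full weight-bearing.** The documents give no rate. Assume exponential times with a proportion p reaching it by 12 months. The rate is λ = −ln(1 − p) / 12, the true median is ln 2 / λ, and the median among those who reach it is −ln(1 − p/2) / λ.

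- p = 0.5: λ = 0.0578; true median 12.0 months, conditional median 5.0.
- p = 0.8: λ = 0.134; true median 5.2 months, conditional median 3.8.

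**The case against.** Several stronger readings are tempting, and the documents do not support them.

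- *A reader might infer that the protocol prescribes Kaplan-Meier for these two variables.* It does not name them. Protocol 12.2.2 analyses bone union as a proportion with a 95% interval and names Kaplan-Meier only for fracture. Both times are SAP additions, so the departure is from the general sentence in 12.1 and not from a named endpoint analysis.
- *A reader might infer a fixed bias of about a quarter.* Suppose 16 of 20 unite by 5 months and 2 more at each of 9 and 12 months. The SAP mean is 3.5 against (16 + 40 + 18 + 24) / 20 = 4.9 with an even split, which is 29% short. With 4 and 12 at the first two visits it is 4.25 against 110 / 20 = 5.5, which is 23% short. In those scenarios every procedure unites and none is censored, so the whole gap comes from ignoring the later visits. A plain mean over all visits would remove it. It does not measure the effect of failed or lost procedures.
- *A reader might infer that the comparison with other devices is distorted.* Protocol 6.2 limits that visual comparison to implant survival, bone union achievement and fracture-free survival. No comparison of healing time is planned.
- *A reader might infer that failures are hidden.* SAP 24.2 gives the number and proportion united with a Clopper-Pearson interval and a listing. Consolidation status is tabulated at each visit from plaster removal on, with reasons requested from the bone consolidation visit when it is not Yes.
- *A reader might infer that fracture has the same gap.* SAP 24.3 already plans Kaplan-Meier. Only its accompanying mean among fractured bones is conditional.

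All five limits stand. They narrow the point but do not rescue the two time summaries, which still describe only procedures with the event and carry no label saying so.

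**Conclusion.** The concern holds in limited form. The times in SAP 24.2 and 24.4 are conditional on reaching the event, and for consolidation on reaching it by the removal or bone consolidation visit. They tend to be short and do not respond to failed healing. At the plan's assumed 80% union, about 4 of 20 procedures leave the consolidation time, and the SAP mean falls 1.55 to 1.85 months below the 12-month restricted mean in the splits tried.

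That size rests on the assumed visit split, on nominal visit dates, and on counting each non-united procedure as 12 months. Medians coincide in some splits, and there is no bias if every procedure reaches the event by Visit 4. The primary endpoint is not touched, and the union proportions do not carry this conditioning. The change is still worth making, because these times will be reported under a secondary endpoint and by severity group.

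**What to change.** In SAP 24.2 and 24.4, analyse time to first event on all FAIS procedures by Kaplan-Meier, or by cumulative incidence with nail removal as a competing event. The second is preferable if any nail is removed before the event, because treating removal as ordinary censoring would overstate cumulative union. State in the text:

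- **Censoring:** a procedure without the event is censored at its last assessment.
- **Late unions:** the 9- and 12-month fields (SAP 20.2 and 21.2) ask whether consolidation was maintained. A first Yes there, with no earlier Yes, counts as the event at that visit.
- **Reporting:** cumulative proportions with 95% confidence intervals and numbers at risk, with a note that events are dated at visits. Kaplan-Meier on visit dates does not remove that coarseness.
- **Conditional means:** keep any mean among procedures with the event, including time to fracture in 24.3, only if it is labelled as conditional and shown with its n.

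SAP 14 should then name these variables beside fracture-free survival. No new data are needed. The cost is two more survival runs in the software already planned, some SAP wording, and healing times that look less favourable.

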24.3 POST TREATMENT FRACTURE-FREE SURVIVAL

The categorical variables to be described are, N and (%) and Clopper-Pearson confidence intervals will be shown at 95.0% as well, for the overall population and for subgroups of patients defined according to OI Type Diagnosis (Mild/Non-deforming / Severe / Highly Severe/Progressively deforming / Lethal) as defined in section 15.6 of this document:

- Number of patients with fracture(s) occurred (variable: "Bone fracture during or after treatment" in adverse event description + confirmation that the bone with fracture is the same where there is the implant*) in at least one procedure
- Number of procedures with fracture(s) occurred (variable: "Bone fracture during or after treatment" in adverse event description + confirmation that the bone with fracture is the same where there is the implant*)

* A list, with confirmation for each AE that the "fracture" is on the same bone or not, will be provided from Sponsor in order to confirm if the bone with fracture is the same where there is the implant.

The descriptive statistic (Mean, SD, Median, Q₁, Q₃, Min, Max) will be shown for the following continuous variable, for the overall population and for subgroups of patients defined according to OI Type Diagnosis (Mild/Non-deforming / Severe / Highly Severe/Progressively deforming / Lethal) as defined in section 15.6 of this document:

- Time to free fracture from surgery (months), per procedure, considered at the first Adverse Event onset date in which variable: "Bone fracture during or after treatment" in adverse event description has been checked. Calculated as the first adverse event onset date with a "Bone fracture during or after treatment" minus date of surgery.

Kaplan-Meier analyses will be provided for Time to free fracture. The median and the 95%CI as well as the number of events and patients censored will be provided.

The number of patients at risk will be displayed.

Event: if "Bone fracture during or after treatment" in adverse event description is clicked (which first occurs).

Time: Time to free fracture from surgery, as has been defined above.

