11.1.5 Possible Adverse Device Effect according to Manufacturer IFU

List of possible Adverse Device Effect expected from Manufacturer IFU (ASADE):

- Non-union, delayed union or malunion
- Superficial infection
- Deep infection
- Bending, breakage or migration of the device
- Bone fracture during or after treatment
- Damage to bone vascularization (e.g. proximal femoral epiphysis)
- Damage to surrounding tissues due to surgical trauma
- Pain, discomfort or abnormal sensations due to the presence of the device
- Possible lesion to the growth plates
- Residual deformities, persistence or recurrence of the initial condition subject to treatment
- Wound healing complications
- Stiffness at surgery site
- Problems related to telescopic functioning
- Events caused by intrinsic risks associated with anesthesia and surgery

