12.2.2 Evaluation of Efficacy

The first efficacy endpoint (Bone union achievement) will be analyzed reporting the number and the proportion of procedures with bone union achieved (Success) together with the relative 95% confidence interval.

The second efficacy endpoint (Post-treatment fracture-free survival) will be analyzed reporting the number and the proportion of procedures with fracture(s) occurred in the treated bone up to 1 year follow-up together with the relative 95% confidence interval.

The cumulative freedom from fracture will be also evaluated using Kaplan-Meier (KM) method, the degree of uncertainty will be expressed with 95% confidence limits (calculated per the method proposed by Greenwood) and a KM graph will be presented along with the number of case-at-risk at exact time points.

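### SAP 24.3 uses two different fracture events in one section, and neither matches the protocol's endpoint of fracture in the treated bone

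*SAP*

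**What the plan says.** Protocol 12.2.2 reports "the proportion of procedures with fracture(s) occurred in the treated bone up to 1 year follow-up", with a 95% confidence interval, and adds a Kaplan-Meier analysis of freedom from fracture under the same endpoint. No AE term enters that definition.

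SAP 24.3 gives two operational rules:

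- **Counts by procedure and by patient.** The AE description must be "Bone fracture during or after treatment", and this is required "in adverse event description + confirmation that the bone with fracture is the same where there is the implant". A footnote leaves the check to the sponsor: a list of whether each break "is on the same bone or not, will be provided from Sponsor in order to confirm if the bone with fracture is the same" (as the one with the nail).
- **Time to fracture and Kaplan-Meier.** The time runs to the first onset date of an AE with that term. The event is the term "in adverse event description is clicked (which first occurs"). Neither definition mentions the bone.

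The term is one of 14 anticipated effects in Protocol 11.1.5. Its neighbours include "Bending, breakage or migration of the device" and "Residual deformities, persistence or recurrence of the initial condition subject to treatment". SAP 23.1.1 adds a category for unanticipated or other events. Each nail has its own eCRF record (Protocol 7.2), records of the same child are linked by an ID reference (Protocol 7.4.2), and a child may contribute one to four procedures (Protocol 12.3). No section says on which nail's record an AE is entered.

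**The concern.** An endpoint analysed in two ways within one section should rest on one event. Here a reader could find a fracture proportion and a one-year Kaplan-Meier estimate that differ because the numerators differ, with nothing in the plan to explain it.

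Both rules also depart from the protocol. The protocol asks whether the treated bone broke. The SAP asks which AE term was chosen, and for the counts it then applies a check that can remove an event but cannot add or reassign one. Protocol 11.1.6 calls repeat fracture the most commonly reported complication of intramedullary nails, and Protocol 6.2 plans a visual comparison of this endpoint with other devices. An event definition that differs from fracture of the treated bone weakens that comparison.

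**Working it through.** The plan states no target or expected figure for this endpoint, so there is none to reproduce. The check sets the rules side by side and then sizes one misclassified fracture.

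**Step 1. Four cases under the three rules, as written**

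| Case | Protocol 12.2.2 | SAP 24.3 counts | SAP 24.3 time and Kaplan-Meier |
|---|---|---|---|
| A. Treated bone, fracture term, correct record | Event | Event | Event |
| B. Bone without that nail, fracture term | No event | No event (confirmation fails) | **Event** |
| C. Treated bone, recorded only under another term | Event | **No event** | **No event** |
| D. Bone with nail B, fracture term, filed on nail A's record | Event for nail B | **None for B**; for A, depends on how the same-bone check is read | **Event for A, none for B** |

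Only case A agrees throughout. Case B makes the two SAP analyses disagree. In case C they agree with each other but not with the protocol. In case D the Kaplan-Meier event is moved to the wrong nail rather than lost. In the counts it is lost if the sponsor checks against the bone on record A, and placed on the wrong procedure if the sponsor accepts any implanted bone.

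Case B is not far-fetched. The AE definition in Protocol 11.1.1 covers events whether or not they are device-related, Protocol 5.1 says fractures can occur in any bone, and the same-bone check itself presupposes that fractures of other bones will carry this term.

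**Step 2. Size of one misclassified fracture**

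Inputs: 20 evaluable nails, 25 with the 20% allowance (Protocol 12.3: 20/(1 − 0.20) = 25); literature repeat-fracture range 11.11% to 37.29% (Protocol 11.1.6); Clopper-Pearson 95% intervals (SAP 14).

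- One fracture: 1/20 = 5 points. If all 25 nails are analysed, 1/25 = 4 points.
- Expected fractures in 20 nails: 20 × 0.1111 = 2.2, and 20 × 0.3729 = 7.5.

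Fracture-free proportion at n = 20, (20 − x)/20 for x recorded fractures:

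| True treated-bone fractures | Two missed | One missed | All correct | One other-bone fracture added |
|---|---|---|---|---|
| 3 | – | 90% (68.3–98.8) | 85% (62.1–96.8) | 80% (56.3–94.3) |
| 7 | 75% (50.9–91.3) | 70% (45.7–88.1) | 65% (40.8–84.6) | 60% (36.1–80.9) |

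Under the SAP as written, the last column can arise only in Kaplan-Meier. The Kaplan-Meier estimate equals the simple proportion only if no nail is censored before one year, and the intervals shown are Clopper-Pearson, not Greenwood.

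**Step 3. Chance of at least one miss (case C), under an assumption**

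Let m be the share of treated-bone fractures filed under another term. The documents give no value, so m = 10% to 30% is assumed. Treating procedures as independent, P(at least one miss) = 1 − (1 − p·m)^20.

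- p = 11.11%: 20% (m = 10%) to 49% (m = 30%).
- p = 37.29%: 53% (m = 10%) to 91% (m = 30%).

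These are illustrations. Nails in one child are not independent, and m could be close to zero.

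**The case against.** The strongest case against is that the misfiling is hypothetical. A plainly worded fracture term exists, and an investigator has little reason to choose another. The eCRF choice list is not shown, and the SAP's references to a term being checked or clicked are compatible with several terms per AE, which would shrink case C. Nail breakage has its own device-deficiency route (SAP 23.2.1). Endpoint variables get 100% source verification (Protocol 14.2), AEs are MedDRA-coded (Protocol 12.5), a full AE listing is produced (SAP 23.1.4), and the later visits ask whether consolidation was maintained (SAP 20.2 and 21.2). The footnote in 24.3 speaks of confirmation for each AE, so the list may be wider than the fracture term. The endpoint is secondary with no decision threshold, and 5 points is small beside an interval of about 44 points (40.8 to 84.6).

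Much of this stands as to frequency and weight: the misfiling share is unknown and may be low. It does not repair the rule. None of those safeguards feeds the event definition in 24.3, and even a list covering every AE would not help while the count still requires the term. Source verification does not settle a choice between two terms that both fit.

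One could also say that the same-bone check was meant to carry over to Kaplan-Meier, whose sentence in the protocol does not repeat the bone. But the SAP defines both the time variable and the event without it. Carrying it over would cure case B only.

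A reader might infer that every misfiling flatters the device. The documents do not support that. In Kaplan-Meier, a fracture of another bone lowers fracture-free survival, and a fracture filed on another nail's record is moved, not lost.

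**Conclusion.** The point holds as an inconsistency of definition and should be corrected before the analysis. Two things follow directly from the text. First, the counts and the Kaplan-Meier analysis in SAP 24.3 use different events. Second, neither is the protocol's event, because a single AE term is the only entry and no step adds or reassigns a fracture.

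The direction is not fixed: Kaplan-Meier can overcount fractures in other bones, and the counts can undercount fractures in treated ones. The size is 5 points per misclassified fracture at 20 nails (4 at 25), against roughly 2 to 7 expected fractures if the literature range applies to this device and horizon. How many would be misclassified cannot be derived from the documents. The loss from overlapping terms rests on the inference that an AE may carry only one term, and it would be smaller with multi-select.

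**What to change.** In SAP 24.3, define the event once: a documented fracture of the bone carrying that JTIN within the one-year follow-up, whatever the AE term and whichever of the child's records holds it.

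Extend the sponsor's planned list to all AEs under four groups: fracture; bending, breakage or migration; residual deformity or recurrence; and Other. Add two columns, fracture yes/no and fractured bone, and complete the list before the analysis. Assign each event to the nail in that bone. Use the same event in the counts, the time variable and the Kaplan-Meier curve.

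The cost is SAP wording and a somewhat longer review of a list already planned, with no new visits or data. The fracture rate may become less favourable as a result.

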10.2.2 Visit 1 - Surgery (Day 0)

The investigator will collect information regarding the applied JTIN and the surgical intervention itself, including the intraoperative application time of fluoroscopy, previous device removal (if applicable) and eventual blood transfusion. The investigator will also collect X-ray/fluoroscopy images, to assess the treatment outcome, and the medication prescribed after the surgery. From this visit and for the rest of the visits, the Investigator will collect information about adverse events (AEs) and medical device deficiency (MDD).

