24 SECONDARY OBJECTIVE

The secondary objective of the study is to evaluate the clinical safety and performance of JTIN by the three following endpoints, when the MD is used within the scope and according to the manufacturer IFU:

- **Implant survival rate: percentage of not exchanged nails up to 1 year follow-up (safety);**
- **Bone union achievement (performance);**
- **Post-treatment fracture-free survival up to 1 year follow-up (performance)**

This analysis will be performed on FAS/FAIS population.

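### SAP 24.3 scores a post-treatment fracture endpoint from an adverse event item that also covers fractures during treatment, and sets no start point, so an intra-operative fracture recorded there would count as an event at time 0

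*SAP*

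**What the plan says.** SAP section 24 lists the endpoint as "Post-treatment fracture-free survival up to 1 year follow-up (performance". Protocol 12.2.2 analyses it as the number and proportion of "procedures with fracture(s) occurred in the treated bone up to 1 year follow-up", together with a Kaplan-Meier curve. That wording gives an end to the observation period but no beginning.

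SAP 24.3 turns this into data rules:

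- **Count:** "Number of procedures with fracture(s) occurred (variable: 'Bone fracture during or after treatment' in adverse event description", with a parallel count of patients. Both add one filter: "A list, with confirmation for each AE that the 'fracture' is on the same bone or not, will be provided from Sponsor".
- **Time variable:** "Calculated as the first adverse event onset date with a 'Bone fracture during or after treatment' minus date of surgery".
- **Kaplan-Meier event:** "Event: if 'Bone fracture during or after treatment' in adverse event description is clicked (which first occurs".

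The item "Bone fracture during or after treatment" is one entry in the list of possible device effects in Protocol 11.1.5. That list has no separate entry for intra-operative fracture. On when collection starts, Protocol 10.2.2 (the surgery visit) says: "From this visit and for the rest of the visits, the Investigator will collect information about adverse events (AEs) and medical device deficiency (MDD".

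**The concern.** The endpoint asks whether the nailed bone stays unbroken after the operation. The variable that scores it is wider by its own wording. A fracture of the treated bone while the canal is drilled or the nail is driven in falls within the collection period, fits the item, and is by definition in the implanted bone. Nothing in SAP 24.3 then separates it from a refracture months later.

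Three results would be affected. The fracture proportion would mix a surgical complication with a failure to protect the bone. The Kaplan-Meier curve could start below 1, and because only the first event is used, a true refracture of the same bone would not appear in it. The mean time to fracture would be pulled toward zero.

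Protocol 6.2 plans a visual comparison of the secondary endpoints with other devices. The relevant literature row in Protocol 11.1.6 is for repeat fractures (11.11% to 37.29%), so the JTIN figure might not be like for like.

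**Working it through.** **The plan's own figures.** The documents give no target or expected value for this endpoint. The sample size in Protocol 12.3 and SAP section 9 rests on the complication and bone-union rates and does not depend on the fracture rule. It supplies only the denominators: 20 evaluable procedures, and 20 / (1 − 0.20) = 25 to be collected.

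**Tracing one intra-operative fracture of the treated bone, recorded under the item:**

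1. Is it within adverse event collection? Yes. Collection starts at the surgery visit (Protocol 10.2.2).
2. Does it fit the item? Yes. The wording includes fractures during treatment.
3. Does it pass the same-bone check? Yes. The check asks where the fracture is, not when it happened. The time variable and the Kaplan-Meier event, as worded, do not repeat even this check.
4. What is its time? Onset date minus surgery date = 0.
5. Is it removed by an onset rule? No. The onset date sets the event time but does not decide whether the event counts.
6. What if the same bone breaks again later? The procedure count does not change, because the procedure is already counted. The Kaplan-Meier event stays at time 0, so the later fracture is lost from the curve.

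**Illustration of size.** The counts are assumed, with no censoring, and each intra-operative fracture is placed in a procedure that has no later fracture. The post-operative counts come from the literature range: 0.1111 × 20 = 2.2, taken as 2, and 0.3729 × 20 = 7.5, taken as 7; for 25 procedures, 0.1111 × 25 = 2.8, taken as 3. Intervals are Clopper-Pearson, as in SAP section 14: the lower limit is the 0.025 quantile of Beta(x, n − x + 1) and the upper limit is the 0.975 quantile of Beta(x + 1, n − x).

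| n | Post-operative | Intra-operative | Rate under SAP 24.3 | 95% CI (%) | Kaplan-Meier start |
|---|---|---|---|---|---|
| 20 | 2 | 0 | 10% | 1.2 to 31.7 | 1.00 |
| 20 | 2 | 1 | 15% | 3.2 to 37.9 | 0.95 |
| 20 | 2 | 2 | 20% | 5.7 to 43.7 | 0.90 |
| 20 | 7 | 0 | 35% | 15.4 to 59.2 | 1.00 |
| 20 | 7 | 1 | 40% | 19.1 to 63.9 | 0.95 |
| 25 | 3 | 0 | 12% | 2.5 to 31.2 | 1.00 |
| 25 | 3 | 1 | 16% | 4.5 to 36.1 | 0.96 |

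Each such fracture adds 1/20 = 5 points, or 1/25 = 4 points. For the mean time, suppose two post-operative fractures occur at t1 and t2. The mean is (t1 + t2)/2 without the time-0 event and (t1 + t2)/3 with it, which is one third lower whatever the two times are.

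**The case against.** A reader might infer that every intra-operative fracture will be scored as a post-treatment fracture. The documents do not establish that. Protocol 11.1.5 also offers an item for tissue damage from the operation and one for the inherent risks of anaesthesia and surgery, and the synopsis lists complications among the surgery details. An investigator could use any of these. The combined fracture item is the natural choice, but no rule directs it, so the statement has to stay conditional. The alternatives do not cure the problem either: without a rule, similar events could be coded differently, and SAP 16.1 tabulates no surgical-complication variable.

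A reader might also infer that requiring onset after the calendar day of surgery would settle the matter. It would not. Treatment is not defined for this endpoint and could be read as running to plaster removal or consolidation. A rule based on date alone would also drop a fracture that happened later on the day of surgery, which is a genuine post-operative event.

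Further points stand in the plan's favour. Counting from surgery is compatible with Protocol 12.2.2, which sets no start. Any bias raises the fracture rate and so works against the device. Onset dates are recorded and SAP 23.1.4 lists every adverse event, so a careful reader of 20 to 25 procedures could spot a Day 0 fracture. No test or threshold depends on the result, and the intervals in the table overlap heavily. These points lower the severity. They do not remove the mismatch between the endpoint's name and its variable, and a listing does not correct a proportion or a curve.

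**Conclusion.** The point holds in conditional form. SAP 24.3 has no start point for post-treatment, and its scoring item is wider than the endpoint. If an intra-operative fracture of the treated bone is recorded under that item, it becomes an event at time 0 and masks a later refracture in the Kaplan-Meier analysis.

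The size is not known. The 5-point step assumes 20 procedures and no later fracture in the same procedure. The documents give no frequency for intra-operative fracture, and the true number may be zero, so the table should not be read as evidence that the reported rate will be materially wrong. The sample size and the definition of the primary endpoint are unaffected. Severity is minor to moderate.

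**What to change.** In SAP 24.3:

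1. State the start point that defines post-treatment, for example after the end of the implantation surgery. The sponsor should choose it, since the documents do not define the term.
2. Apply it identically to the patient count, the procedure count, the time variable and the Kaplan-Meier event, using the first fracture that qualifies. A refracture after an intra-operative fracture then enters the curve.
3. Add an intra-operative yes/no column to the same-bone confirmation list that the sponsor already provides, so that Day 0 fractures are classified by event and not by date alone.
4. Report intra-operative fractures of the treated bone on a separate line. Those judged certainly or possibly related stay in the primary adverse event rate.

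The cost is a few lines of SAP text and one extra classification per fracture event. Onset and surgery dates are already used in SAP 24.3, so no new patient data should be needed beyond that classification. The rule should be fixed before the fracture results are examined; if that is no longer possible, Protocol 12.1 already requires deviations from the statistical plan to be documented in the study report.
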